16.1 INTERIM ANALYSIS AND STOPPING RULES

There is no planned interim analysis for the primary endpoint until sufficient data has been accrued and by the time this is achieved the recruitment should be complete. Similarly, there is no planned stopping rules for this trial because evidence from our own internal clinical audit data suggests that study participants are in no additional risks since these procedures are the standard.

16.2 SUBGROUP ANALYSES

Subgroup analyses will be performed at the end of the study to establish the impact of potential confounding factors that may determine ICU stay such as infection, antibiotic usage, re-operation or re-opening of chest in ICU, postoperative anaemia, thrombocytopenia, hypoalbuminemia, post-operative bleeding and post-operative pulmonary complications.

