There are several potential explanations for such a high morbidity and mortality. It has been suggested that oxidative stress induced by cardiac surgery is involved in the pathogenesis of an underlying systemic inflammatory response (SIRS) experienced by most patient's perioperatively [9, 10]. This leads to a further reduction in antioxidant capacity and an increased onset of a cascade of events such as protein modification, lipid peroxidation, and the activation of circulating blood leukocytes. Some studies have also suggested transient endotoxemia as a major stimulus for the development of SIRS in these patients [11-13]. However, the pathogenesis involved in this phenomenon is not entirely clear. The association between perioperative renal impairment and mortality has been shown in several retrospective studies [14-17].

A recent randomised study demonstrated that both intraoperative haemofiltration and steroids attenuate the inflammatory response but only haemofiltration reduced time to tracheal extubation for adults after cardiopulmonary bypass [17]. In addition, another non-randomised study [18] demonstrated that haemofiltration during CPB attenuates postoperative anaemia, thrombocytopenia and hypoalbuminemia, may reduce post-operative bleeding and appears to decrease post-operative pulmonary complications. Also others [19] showed that the combined use of balanced ultrafiltration and modified ultrafiltration can effectively concentrate the blood, modify the increase of some harmful inflammatory mediators, and attenuate lung oedema and inflammatory pulmonary injury that

mitigates the impairment of pulmonary function. In view of the evidence that has shown that the use of haemofiltration during cardiopulmonary bypass reduces time to tracheal extubation, length of mechanical ventilation and attenuates postoperative anaemia, thrombocytopenia, hypoalbuminemia, post-operative bleeding and post-operative pulmonary complications, we hypothesise that this would be the basis for a reduction in ICU stay, perioperative complications and overall length of hospital stay, hence the objective of this proposal.

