7. PLANNED TRIAL INTERVENTIONS

Patients that fulfil inclusion and exclusion criteria will be asked to give consent for the study at least a day before surgery and will be randomised into either of the two study groups on the day of surgery as follows:

1. ON-pump coronary artery bypass graft (CABG) surgery patients with GFR<60 ml/min without haemofiltration (control group)
2. ON-pump CABG surgery patients with GFR <60 ml/min undergoing haemofiltration (Experimental group)

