9. RANDOMISATION

Random block sizes of 2, 4, and 6 will ensure numerical balance between the two groups. Patients will be stratified at the design stage on the basis of diabetes mellitus and the level of eGFR (eGFR < 40 > 15 ml/min *versus* eGFR > 40 < 60 ml/min). The randomisation service will be available 09:00 – 17:00 (UK time). Once randomised, the patient will be enrolled into the study and data will contribute to the primary outcome.

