10. PROTECTING AGAINST OTHER SOURCES OF BIAS

It is very difficult to disguise the evidence of intraoperative haemofiltration during cardiopulmonary bypass. Although it is relatively easy to put up a haemofilter onto the pump

and prime it to look as if it is being run in the non-haemofiltration group there is other evidence such as the 5 L bags of “Accusol 35” that need to be hanging up and vac sacs full of waste solution that cannot be disguised. The surgeon may not ‘know’ which arm a patient is randomised to, but it would be nearly impossible to blind them from noticing the presence of vac sacs full of waste solution which is indicative of the haemofiltration procedure. Hence, only the patients are likely to be blinded as to whether zero-balance filtration has been applied. Discharge from ICU is based on Nurse Discharge Guidelines which are independent of ITU physicians and follows a scoring system termed “Modified Early Warning Score - MEWS” ranging from 0-3 days. Nurses discharge patients from ICU when the MEWS is <2.0 and that only consultant cardiac surgeons/intensivists are authorised to discharge a patient out of ITU when the total MEWS is >3.0. All ICU staff will be blinded as to whether or not the patient received intraoperative haemofiltration to eliminate bias.

Incidences such as infection, antibiotic usage, re-operation or re-opening of chest in ICU, postoperative anaemia, thrombocytopenia, hypoalbuminemia, post-operative bleeding and post-operative pulmonary complications which are potential confounding factors that determine ICU stay will be documented.

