14. STUDY OUTCOMES

Proposed Outcome Measures: These will be evaluated for suitability and reliability for the main trial - Our chosen primary outcome and secondary outcome measures will be monitored to ensure they are suitable and reliably informative of the impact of intraoperative haemofiltration. There is an element of concern that the outcomes could be confounded by crossovers between the experimental groups, in response to protocol deviation by clinicians. All protocol deviations will be documented in the database. The primary analysis will be completed on an intention to treat basis but separate information will be provided on the incidence and rate of protocol deviation and crossover. We will also report a range of other outcomes including key measures of resource utilisation and kidney function at 6 weeks follow-up to establish whether these may be suitable for the main trial. The outcome measures to be evaluated are:

PRIMARY OUTCOMES

Incidents of ICU stay >3 days for patients with renal impairment identified as an estimated glomerular filtration (eGFR) <60 ml/min.

SECONDARY OUTCOMES

CLINICAL OUTCOMES

- Composite of perioperative incidences: Bleeding, sepsis, death, arrhythmias, stroke, and myocardial infarction
- Need for postoperative continuous veno-venous haemofiltration (CVVH) in the ICU - Indications for requirement of postoperative continuous veno-venous haemofiltration must adhere to our **surgical guidelines**.
- Mechanical ventilation time
- Hospital stay
- eGFR at 6 weeks follow-up

SECONDARY ECONOMIC OUTCOMES: Resource utilisation and key costs indicators associated with each of the two pilot arms specifically ICU stay and hospital stay, postoperative renal replacement therapy, mechanical ventilation, medications, will be estimated up until hospital discharge. Participants will be required to complete health-related quality of life questionnaire EQ-5D at hospital admission before surgery and at the 6 weeks follow-up hospital visits.

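### Section 16.2 treats eight post-randomisation events as confounders, so treatment comparisons within those subgroups would not be randomised comparisons

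*Protocol*

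**What the plan says.** Section 16.2 sets the aim: "Subgroup analyses will be performed at the end of the study to establish the impact of potential confounding factors that may determine ICU stay". The examples given are "infection, antibiotic usage, re-operation or re-opening of chest in ICU, postoperative anaemia, thrombocytopenia, hypoalbuminemia, post-operative bleeding and post-operative pulmonary complications". Section 10 has the same list, describes the items as incidences, and says of them "which are potential confounding factors that determine ICU stay will be documented".

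Three other places bear on this:

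- **Timing.** Under Section 7, patients "will be randomised into either of the two study groups on the day of surgery". Section 7.2 applies haemofiltration during bypass.
- **Mechanism.** Section 5.1 cites evidence that haemofiltration during bypass "attenuates postoperative anaemia, thrombocytopenia, hypoalbuminemia, post-operative bleeding and post-operative pulmonary complications", and continues: "we hypothesise that this would be the basis for a reduction in ICU stay, perioperative complications and overall length of hospital stay".
- **Outcomes.** Section 14 gives the primary outcome as "Incidents of ICU stay >3 days for patients with renal impairment identified as an estimated glomerular filtration (eGFR) <60 ml/min". Bleeding and sepsis are components of the secondary perioperative composite.

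Sections 14 and 16 make intention to treat the primary analysis. Section 9 names two baseline stratifiers: "Patients will be stratified at the design stage on the basis of diabetes mellitus and the level of eGFR".

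**The concern.** A confounder is a common cause of treatment and outcome. Allocation here is random, and the listed events follow it, so none of them can have influenced who received haemofiltration. Where treatment changes an event and the event changes ICU stay, the event is a mediator. Section 5.1 claims exactly that for five of the eight, so Sections 5.1 and 16.2 assign the same variables incompatible roles. Bleeding is also a secondary outcome component, which makes it both an outcome and a definition of subgroups.

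If the arms are compared within such subgroups, two things go wrong. The part of the effect that runs through the event is removed. And the patients who have the event under treatment may differ in prognosis from those who have it under control, which brings in selection bias. A reader of the pilot could then be misled about the effect on ICU stay, or about which outcomes suit the main trial, a judgement that Section 14 says the pilot is meant to inform.

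**Working it through.** **1. Causal role of each listed factor**

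- Postoperative anaemia, thrombocytopenia, hypoalbuminaemia, bleeding, pulmonary complications: after randomisation, and named in Section 5.1 as attenuated by haemofiltration. Mediators on the protocol's own account.
- Infection, antibiotic usage, re-operation or re-opening: not named in that mechanism. In the context of Section 10 they are events of the postoperative course, so they too follow randomisation.
- None of the eight is a baseline factor.

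**2. The protocol's own figure**

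The concern rests on no stated figure, but the illustrations borrow the 18% and 12% of Section 13, so I checked the calculation there. With a pooled variance, two-sided 0.05 and 80% power:

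n per arm = [1.96 × √(2 × 0.15 × 0.85) + 0.8416 × √(0.18 × 0.82 + 0.12 × 0.88)]² / 0.06² = 555

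That is 1110 in total against the stated 1112, so it reproduces.

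**3. Effect hidden (assumed rates)**

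Let M be a postoperative complication and let treatment act only through M. Assume the risk of ICU stay over 3 days is 42% with M and 2% without M in both arms, and that M falls from 40% to 25%.

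- Control: 0.40 × 0.42 + 0.60 × 0.02 = 0.18
- Treated: 0.25 × 0.42 + 0.75 × 0.02 = 0.12
- Overall difference: −6 points
- Difference with M: 42% − 42% = 0; without M: 2% − 2% = 0

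The same happens with risks of 50% and 5% (M from 28.9% to 15.6%) and of 60% and 6% (M from 22.2% to 11.1%).

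**4. Effect reversed (assumed rates)**

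Assume 30% of patients are frail, and that frailty is unmeasured. M occurs in 40% of the frail in both arms; in the non-frail it falls from 35% to 8%. The risk of a long ICU stay is 35% (non-frail) or 55% (frail) with M, and 3% or 8% without.

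- P(M), control: 0.70 × 0.35 + 0.30 × 0.40 = 0.365
- P(M), treated: 0.70 × 0.08 + 0.30 × 0.40 = 0.176
- Risk with M, control: (0.245 × 0.35 + 0.12 × 0.55) / 0.365 = 41.6%
- Risk with M, treated: (0.056 × 0.35 + 0.12 × 0.55) / 0.176 = 48.6%
- Risk without M: control 0.02805 / 0.635 = 4.4%; treated 0.03372 / 0.824 = 4.1%
- Overall: control 0.15175 + 0.02805 = 18.0%; treated 0.08560 + 0.03372 = 11.9%

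Treatment lowers the overall risk by about 6 points, yet patients with M show +7.1 points on unrounded figures. Selection alone produces this: the frail are 0.12 / 0.365 = 33% of control patients with M but 0.12 / 0.176 = 68% of treated patients with M.

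The affected subgroup depends on the assumptions. Take M in 70% of frail and 25% of non-frail controls, multiplied by 0.6 under treatment, and outcome risk 0.03 + 0.25 for M + 0.20 for frailty. Overall risk is then 18.6% against 14.8%, but among patients without M it is 5.9% against 7.5%, an apparent harm of 1.6 points.

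**5. What 60 patients can show**

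With 30 per arm (equal allocation assumed), expected primary events are 30 × 0.18 = 5.4 and 30 × 0.12 = 3.6, about 9 in all. Power for 18% against 12% is about 9%. Any subgroup split would divide those 9 events further.

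**The case against.** The strongest reply is that Section 16.2 states an interest in how these events affect ICU stay and does not say that arms will be compared within each of them. A prognostic reading is open, and it would fit a feasibility pilot that is judging its outcome measures. That reading is possible, but it sits poorly with a subgroup heading and a confounder label inside the planned analyses of a randomised comparison. If description was meant, the text should say so. Nor is this a detail left to an analysis plan: the protocol itself chooses the variables and gives them the wrong role.

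Several limits do stand:

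- A reader might infer that the trial's main effect estimate is compromised. It is not: the primary analysis is by intention to treat and conditions on none of these events.
- A reader might infer that the protocol names all eight factors as the mechanism. Section 5.1 names five. The other three are unsuitable because they arise after randomisation, not because they are stated mediators.
- A reader might take the illustrated reversals as forecasts. Every complication rate, conditional risk and frailty figure is assumed, and with about 9 expected events differences of this size could not be told from chance in the pilot.
- The absence of diabetes and eGFR from Section 16.2 is not a fault in itself. The list there is given as examples, and baseline subgroups may be specified elsewhere.
- Recording these events, as Section 10 plans, is harmless and needed. Only the label is wrong there.

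**Conclusion.** The concern holds for Section 16.2 and for any use of its results to interpret the effect on ICU stay or to plan the main trial. All eight factors follow randomisation, and for five of them the confounder label contradicts the mechanism in Section 5.1. Treatment comparisons within these subgroups would be open to bias. Under assumed rates, an overall 6-point reduction can appear as no difference in either subgroup or as a 7.1-point excess among patients with the complication. Those values establish possibility only; the protocol gives no complication rates, so neither the size nor the direction of the bias here can be derived.

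Severity is moderate. It might be tempting to rate this as something that must be put right before the trial can be relied on. The documents do not support that for a secondary, end-of-study analysis in a 60-patient feasibility pilot whose primary analysis is untouched.

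**What to change.** Revise Section 16.2 as follows:

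1. Report each listed event by randomised arm, as an outcome.
2. Restrict any treatment-effect subgroups to baseline factors. The randomisation stratifiers, diabetes and eGFR band, are available. Give treatment-by-factor interaction estimates with 95% confidence intervals, labelled exploratory, and state that they will be very imprecise in 60 patients.
3. Label any analysis relating the listed events to ICU stay as exploratory prognostic or mediation work, with its assumptions stated, and not as adjusted efficacy.
4. In Sections 10 and 16.2, replace the confounder label with post-randomisation events.

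The cost is wording only. Section 10 already has the events documented, the stratifiers are known at randomisation, and neither the sample size nor the primary analysis changes.

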17. SAFETY REPORTING

The study procedures adapted here are part of normal clinical practice. Safety will be assessed by tracking the number and percentage of adverse events (AEs) up to discharge from hospital. Serious and other adverse events will be recorded and reported in accordance with the International Conference for Harmonisation of Good Clinical Practice (ICH GCP) guidelines/the European Clinical Trials Directive 2001/20/EC and the Sponsor's Research Related Adverse Event Reporting Policy. ICH GCP requires that both investigators and sponsors follow specific procedures when reporting adverse/reactions in clinical trials. All serious adverse events **must** be reported to the steering committee and documented in CRFs. Such events result in death or are life-threatening, require hospitalisation or prolongation of existing hospitalisation, result in persistent or significant disability or incapacity or may have created a congenital anomaly or birth defect

Examples would include, but are not limited to:

- **Deaths related or unrelated to healthcare-acquired infection**
- **Life-threatening bleeding**
- **Intracranial haemorrhage**
- **Cerebrovascular accident**
- **Profound thrombocytopenia (platelet counts $\leq 50,000/\text{mm}^3$)**
- Allergic reactions

17.1 ADVERSE EVENT

Any untoward medical occurrence in a patient or clinical trial subject to whom a medicinal product has been administered including occurrences which are not necessarily caused by or related to the product.

17.2 ADVERSE REACTION

Any untoward and unintended response to an investigational product related to any dose administered.

17.3 UNEXPECTED ADVERSE REACTION

An adverse reaction, the nature or severity of which is not consistent with the information about the device or medicinal product in question set out in the summary of product characteristics (or investigator brochure) for that product).

18. MAJOR PROTOCOL VIOLATION

Major protocol violations will be documented including: failure to ensure adequate informed consent, recruitment of ineligible patient into the study on the basis of the inclusion and exclusion criteria and incorrect randomisation of a patient such that the patients are entered into the wrong treatment arm for clinical reasons. During the course of the trial, protocol deviations will be tracked.

19. INDEMNITY AND INSURANCE

The Liverpool Heart & Chest Hospital NHS Trust is covered under the standard NHS indemnity sponsorship for the study.

20. RESEARCH GOVERNANCE

The Liverpool Heart & Chest Hospital NHS Trust as the sponsor for this trial will ensure that the rights, safety, and wellbeing of participants will be safe guarded. Issues of consent and confidentiality are paramount in line with the *MRC Guidelines for Good Clinical Practice in Clinical Trials*. Individual patient medical information obtained as a result of this study is considered confidential and disclosure to third parties is prohibited. Patient confidentiality will be further ensured by utilising patient-identification code numbers to correspond to treatment data in the computer files. With appropriate patient authorisation, medical information may be given to the patient's personal physician or to other appropriate medical personnel responsible for his/her treatment. Data generated as a result of this trial are to be made available for inspection on request by the participating physicians, by the Ethics Committee and the regulatory authorities.

21. ETHICAL ARRANGEMENTS

The protocol will be conducted according to the principles of the Declaration of Helsinki (www.wma.net) and Good Clinical Practice, NHS Research Governance (www.doh.gov.uk), the EU and the NHS Governance Framework. The study will be sponsored by the Liverpool Heart & Chest Hospital NHS Trust. The trial protocol will be approved by an internal review board and via the Integrated Research Application System. Approval from the ethics committee will be obtained if the consent form is updated or amended whenever new information becomes available that may be relevant to the patient. Patient's right to privacy will be respected at all times to comply with the Data Protection Act 1998 and Caldicott

Principle. Medical records may be inspected for monitoring auditing purposes by individuals from the Clinical Trials Unit, Liverpool Heart & Chest Hospital NHS Trust. Patients consent to this as part of the written informed consent process. All electronic information will be stored in a password protected NHS computer.

21.1 RISKS AND ANTICIPATED BENEFITS FOR TRIAL PARTICIPANTS AND SOCIETY, INCLUDING HOW BENEFITS JUSTIFY RISKS

There evidence to suggest that over 20% of patients elective for cardiac surgery has preoperative renal impairment that increases operative risk of death. One of the modalities currently in practice aiming to alleviate this problem is intraoperative haemofiltration support. However, there is a widespread variability in clinical practice within cardiac surgery units worldwide on the use of haemofiltration on a case-by-case basis. Although haemofiltration is widely used, its effectiveness as a prophylactic therapeutic tool for renal impairment during the intraoperative phase whilst the patient is on cardiopulmonary bypass remains un-tested in randomised trials and no evidence from prospective randomised studies is available to demonstrate risks associated with its application. The possible risks of taking part are likely to be common to all patients with impaired kidney function scheduled to undergo cardiac surgery. We anticipate that the risks associated with the trial are outweighed by potential benefits to the patients and society as whole as follows:

1. Reduction in NHS costs by cutting overall ICU treatment costs- Currently, the cost of an intraoperative haemofiltration is approximately £200 a patient which is only 3-4% of what it would cost to perform postoperative continuous veno-venous haemofiltration or dialysis in intensive care units (ICU)/high-dependent units (up to £5000-£6000 a patient over and above standard costs). If the study can establish that intraoperative haemofiltration for patients with renal impairment is effective at reducing the likelihood of postoperative haemofiltration, length of stay in ICU and hospital this will represent an important treatment strategy that could save the NHS millions of pounds every year. Thus there is potential for this study to influence clinical decision making, identify the level of care required to reduce length of stay in ICU and hospital for patients, improve overall operative outcomes and reduce treatment costs.
2. There is also potential for increasing capacity by freeing more ICU beds (wherever the care is carried out) and wards consequently allowing more operations to be performed in the same amount of time.

3. There is also a potential for a reduction in the number of cases that might otherwise go on to develop acute kidney injury, permanent renal damage/ chronic renal failure that would necessitate further long-term use of NHS resources.

21.2 INFORMING POTENTIAL TRIAL PARTICIPANTS OF POSSIBLE BENEFITS AND KNOWN RISKS

The patient will be given **patient information sheets** and allowed time to study them (at least a day). Potential trial participant will be informed of the potential benefits and known risks at the time when consent is being sought.

21.3 OBTAINING INFORMED CONSENT FROM PARTICIPANTS WHENEVER POSSIBLE OR PROPOSED ACTION WHERE FULLY INFORMED CONSENT IS NOT POSSIBLE

In line with DIRECTIVE 2001/20/EC OF THE EUROPEAN PARLIAMENT of 2001 all research patients are required to provide written informed consent before enrolment in a trial. Potential participants in this study will be no exceptional.

In summary, the research protocol will be approved in advance by our institutional research & development Committee. Before obtaining informed consent, information will be given in a language and at a level of complexity understandable to the patient in both oral and written form by the investigator or designee. Patients will not be coerced or unduly influenced in order for the patient to participate or remain in the trial and will be given ample time and opportunity to inquire about details of the trial and all questions about the trial should be answered to their satisfaction. If the patient is unable to read the consent form, a witness should be present during the entire informed consent discussion process. After the informed consent form is read to and signed by the patient, they must then be given a copy of the signed and dated informed consent form. Patients that decline consent at this stage will not be included in the study and their results will not be used. However, data on the total number deemed eligible for the study and the proportion of these subjects proceeding to randomisation will be documented. Patient will be informed that they may withdraw or discontinue from the study anytime without giving an explanation and that their action will not affect their standard of care. Patient's that die after randomisation will have their data included in the final analysis, unless legal representatives raise objections.

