8. STUDY POPULATION AND RECRUITMENT STRATEGY

Patients from the routine waiting list for CABG operations will be pre-screened for inclusion/exclusion criteria and will be informed about the trial by the investigators during their initial visit to the hospital for investigations. Eligible patients will be asked to sign a written consent form by the consultant in receipt of the initial referral or research nurse at the time of their surgical outpatient visit. In-patients will be given at least 12-24 hours time to study the patient information and consent will be sought **on the day before the operation**. Patients will only enter the active phase after having provided informed written consent and are included in the trial register. Patients that drop out prior to randomisation after registration will be logged on to the CONSORT diagram but not included in the intention-to-treat analysis.

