13. PROPOSED SAMPLE SIZE

Calculation of an accurate samples size at this stage would not be precise since this is a pilot feasibility study. However, existing data accrued from our audit department suggest that, at the Liverpool Heart & Chest Hospital, incident rates for intensive care unit (ICU) stay >3 days for patients with estimated GFR <60 ml/min after isolated coronary artery bypass graft (CABG) surgery in years between 2002 and 2008 were 18%. We estimate that even if the proportion of these patients that stay in ICU for > 3 days is reduced to at least a mean of 12% because of intraoperative haemofiltration, this will be of significant clinical and economic benefit to the NHS. We have estimated that at 80% power (2-sided $\alpha=0.05$), 1112 patients with GFR <60 ml/min will need to be randomised in the main definitive study to detect a reduction in the mean incidents from 18% to 12%. Our plan in this pilot trial is to investigate whether it is feasible to randomise 60 patients in a period of 6 months in a recruitment rate of 10 patients per month from our centre. This complies with previous recommendation for good practice that pilot randomised control trials should recruit a minimum number of 60 patients [24]. The results from this pilot data will allow us to calculate a more accurate sample size and trial duration and/or the number of recruiting centres that would be required for the main trial.

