16. PLANNED ANALYSES

Intention to treat will be considered as the primary analysis. The clinical and economic impact of intraoperative haemofiltration versus no haemofiltration treatment will be examined. Analysis of the primary endpoint and other continuous data will be performed by using a 2-sided unpaired t-test or an equivalent non-parametric test. Categorical secondary outcome measures will be examined using a Chi-square test or Fisher's exact test as required. The potential cost differences per patient will be estimated with confidence intervals. Exploratory analysis will be undertaken using Bayesian Value of Information methods described by Tan and Smith [25] that balances the benefit of detecting a minimally significant difference with at least a given power against the costs of the patient sample size and/or the risk that the research poses to patients. The result of this analysis will provide guidance on the optimal sample size to use in a future RCT that would seek to evaluate the impact of haemofiltration on healthcare costs.

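### Section 21.3 allows a randomised patient's data to be left out of the final analysis only if the patient has died, which contradicts the intention-to-treat analysis in Sections 9, 14 and 16

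*Protocol*

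**What the plan says.** Four parts of the protocol bear on who is analysed.

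- Section 9 (Randomisation): "Once randomised, the patient will be enrolled into the study and data will contribute to the primary outcome". No exception is given.
- Section 14 (Study outcomes): "The primary analysis will be completed on an intention to treat basis".
- Section 16 (Planned analyses): "Intention to treat will be considered as the primary analysis".
- Section 21.3 (Obtaining informed consent): "Patient's that die after randomisation will have their data included in the final analysis, unless legal representatives raise objections".

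The only other exclusion linked to the intention-to-treat set is in Section 8: "Patients that drop out prior to randomisation after registration will be logged on to the CONSORT diagram but not included in the intention-to-treat analysis". That one acts before randomisation and is compatible with intention to treat.

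The primary outcome in Section 14 is "Incidents of ICU stay >3 days for patients with renal impairment identified as an estimated glomerular filtration (eGFR) <60 ml/min". Death is not part of it, but it is a named component of the first secondary clinical outcome: "Composite of perioperative incidences: Bleeding, sepsis, death, arrhythmias, stroke, and myocardial infarction".

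**The concern.** The sentence in Section 21.3 sits among the consent arrangements, but it expressly governs the final analysis, so it acts as a rule for the analysis set. Under it a patient can leave that set after randomisation, and only patients who have died are open to this route. Exclusion therefore depends on an outcome of the trial. It is also distinct from a patient's own withdrawal, which the same section covers separately: these patients gave written consent before they were randomised.

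Nothing else in the protocol limits the effect. No section restricts an objection to future data collection, keeps what has already been collected, asks for removals to be counted by arm, or says how removed patients are handled. A later analysis plan could add a sensitivity analysis, but it could not restore data that the protocol has allowed to be taken out.

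Section 13 says the pilot data will be used to recalculate the sample size of the main trial, so distorted outcome rates would carry forward.

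**Working it through.** **Inputs.** Section 13 gives 60 patients and assumed rates of ICU stay above 3 days of 18% and 12%. Section 9 aims at numerical balance, so about 30 per arm. Expected events are 0.18 × 30 = 5.4 and 0.12 × 30 = 3.6. The protocol gives no death rate and no rate of objections. Everything below about removals is therefore an assumed illustration.

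**The plan's own figure.** Section 13 states 1112 patients for 18% versus 12%, 80% power, two-sided 5%. With the pooled-variance formula for two proportions (mean rate 0.15):

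n per arm = [1.960 × √(2 × 0.15 × 0.85) + 0.842 × √(0.18 × 0.82 + 0.12 × 0.88)]² / 0.06² = 554.8, so 555 per arm and 1110 in total.

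This agrees with 1112 to within 2. The present point does not depend on it.

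**Effect of one removal on an arm with x events in 30.**

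- Removed patient was an event: (x − 1)/29 − x/30 = −(30 − x)/870, a fall whenever x < 30.
- Removed patient was a non-event: x/29 − x/30 = x/870, a rise whenever x > 0.

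**Primary outcome, x = 5 (16.7%).**

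| Removed patient | Rate after removal | Shift |
|---|---|---|
| Stayed more than 3 days, then died (event) | 4/29 = 13.8% | −25/870 = −2.9 points |
| Died before day 3 (non-event as the outcome is written) | 5/29 = 17.2% | +5/870 = +0.6 points |

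With two removals of the same kind, the rates are 3/28 = 10.7% and 5/28 = 17.9%.

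**Difference between arms.** Take 5/30 in control and 4/30 in the experimental arm, a difference of 3.3 points. Removing one experimental patient who was an event gives 3/29 = 10.3% and a difference of 6.3 points. Removing one who was a non-event gives 4/29 = 13.8% and a difference of 2.9 points.

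**Composite.** A perioperative death is always an event, so only the first formula applies. The direction is fixed: the composite rate in that arm falls.

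**How removed patients could be counted.** If the single removed patient had stayed more than 3 days, 4 events remain among 29. Restoring the denominator gives 4/30 = 13.3% (best case) to 5/30 = 16.7% (worst case). If the patient died before day 3, 5 events remain among 29, giving 5/30 = 16.7% to 6/30 = 20.0%. Both ranges contain the true 16.7%. Counting every removed patient as a primary event would give 20.0% in the second case, which is wrong.

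**The case against.** The best defence is that inclusion is the default. Intention to treat is broken only if a patient dies and a representative objects, and in a 60-patient pilot that may never happen. The pilot is also about feasibility. At 18% versus 12% with 30 per arm, the 95% half-width for the difference is 1.96 × √(0.18 × 0.82/30 + 0.12 × 0.88/30) = 0.18, or about 18 points, so no efficacy conclusion would turn on a 2.9-point shift. This stands as a limit on practical weight. It does not remove the contradiction, because imprecision does not excuse an exclusion that depends on outcome.

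A reader might infer more than the documents support, in four ways.

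- *That removing deaths always lowers the primary event rate.* It does so only for patients who had already stayed more than 3 days. For earlier deaths the rate rises. A fixed direction holds only for the composite.
- *That relatives would know the allocation, so objections would differ by arm.* Section 6 calls the trial open-label, but Section 10 expects patients to be blinded and says all ICU staff will be. Section 12 says patients will not know their allocation when they wake. Nothing is said about relatives. The point does not need this mechanism.
- *That the safety count would be corrupted.* Section 17 requires all serious adverse events to be reported to the steering committee and documented in the case record forms, and Section 15 has them monitored from randomisation to discharge. The exception concerns the final analysis and does not suspend that reporting.
- *That the patient's consent overrides a representative's objection in law.* The protocol does not settle this.

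**Conclusion.** The concern holds. Section 21.3 contains an outcome-dependent exclusion after randomisation that cannot be reconciled with Sections 9, 14 and 16, and no other part of the protocol neutralises it. Each removed perioperative death deletes a certain composite event. For the primary outcome, one removal from an arm with 5/30 events shifts the rate by −2.9 or +0.6 points, depending on whether the patient had stayed more than 3 days.

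These sizes rest on 30 patients per arm, 5 events in the arm, one death with an objection, and a death before day 3 counting as a non-event. The actual number of removals cannot be estimated from the protocol and is probably small. The point is worth correcting because the rule is wrong as written and the correction is cheap. It does not mean that the pilot's results will be materially distorted.

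**What to change.** Replace the conditional clause in Section 21.3 with a statement that data collected up to death under the patient's own written consent stay in the intention-to-treat analysis, and align the patient information with it. The sponsor should confirm with the ethics committee that this is permissible, since the protocol does not settle the legal position.

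Add a provision for the case in which removal is nevertheless legally required:

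- report the number of patients removed, by arm;
- for ICU stay above 3 days, give a best-case/worst-case sensitivity analysis with the removed patients restored to the denominator, and do not count them all as events;
- for the composite, count removed perioperative deaths as events.

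The cost is a few sentences in the protocol, matching text in the patient information, and possibly an ethics amendment. No sample-size figure changes.
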